6.6 HANDLING OF MISSING DATA AND OUTLIERS

Handling of missing data and outliers will be performed as described in CTP, Section 7.5.

The only exceptions where imputation might be necessary for safety evaluation are AE dates. Missing or incomplete AE dates are imputed according to BI standards (see BI-KMED-BDS-HTG-0035) (3).

Missing data and outliers of PK data are handled according to BI standards. PK parameters that cannot be reasonably calculated based on the available drug concentration-time data will not be imputed.

Section 7.5 of the CTP: *Missing baseline laboratory values will be imputed by the respective values from the screening visit.*

6.7 BASELINE, TIME WINDOWS AND CALCULATED VISITS

The baseline value is defined as the last measurement before first administration of BI 836880 (= value at V2, in case no actual time is given in data).

Section 5.1 of the CTP: *For the endpoints, baseline is defined as the value at Visit 2; if not measured at Visit 2 then baseline is the value at Visit 1.*

The acceptable time windows for visits are given in the CTP Flow Chart.

Adherence to time windows will be checked via the consistency check listings at the MQRM/RPM/DBLM.

To utilize all available data, including values collected between protocol-specified visit windows and unscheduled visits, time intervals will be defined for analysis of efficacy data. If multiple values are recorded within a visit interval, the value collected closest to the planned visit date will be included in analyses of efficacy endpoints (CSFT, BCVA, and responder analysis) and IOP.

Unscheduled measurements of laboratory data and vital signs data will be assumed to be repeat measurements of the most recent scheduled measurement (e.g. for follow-up or confirmation of a particular value). Therefore, unscheduled measurements will be assigned to the planned time point of the previous scheduled measurement.

Table 6.7: 1 Visit intervals for efficacy endpoints (CSFT, BCVA, responder analysis) and IOP

| Visit | Planned day | Interval Definition | | Visit description |
|--------------|--------------------|----------------------------|----------------------|--------------------------|
| | | From (day) | To (day) | |
| 1 | -28 to -3 | NA | -1 | Screening |
| 2 | 1 | 1 | 1 | Baseline |
| 3 | 29 | 2 | 43 | Week 4 |
| 4 | 57 | 44 | 71 | Week 8 |
| 5 | 85 | 72 | 99 | Week 12 |
| 6 | 113 | 100 | 127 | Week 16 |
| 7 | 141 | 128 | 155 | Week 20 |
| 8 | 169 | 156 | Last assessment date | Week 24 |

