### **Hepatic injury**

A hepatic injury is defined by the following alterations of hepatic laboratory parameters:

- an elevation of AST and/or ALT  $\geq$  3 fold ULN combined with an elevation of total bilirubin  $\geq$  2 fold ULN measured in the same blood draw sample, and/or
- aminotransferase (ALT, and/or AST) elevations  $\geq$  10 fold ULN

These lab findings constitute a hepatic injury alert and the patients showing these lab abnormalities need to be followed up according to the “DILI checklist” provided in the eDC system.

In case of clinical symptoms of hepatic injury (icterus, unexplained encephalopathy, unexplained coagulopathy, right upper quadrant abdominal pain, etc.) without lab results (ALT, AST, total bilirubin) available, the investigator should make sure these parameters are analysed, if necessary in an unscheduled blood test. Should the results meet the criteria of hepatic injury alert, the procedures described in the DILI checklist should be followed.

All AEs meeting the criteria for a dose limiting event as defined in [Section 5.2.1](#) are defined as AESIs for this trial.

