**Withdrawal of consent**

If a patient is not willing to continue in the trial and want to withdraw consent prior to the end of the trial, Visit 7 should be scheduled as soon as possible, and also Visit 8/EOT should be performed to assess for safety.

If patient refuses to participate at a Visit 7 or Visit 8, the trial completion page of the eCRF has to be filled in.

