7.8.2 Laboratory data

The analyses of laboratory data will be descriptive in nature and will be based on BI standards [BI-KMED-BDS-HTG-0042] (8).

Descriptive statistics of laboratory data including change from baseline will be calculated by visit based on the worst value of the patient at that visit (Or assigned to that visit / planned time point).

Additionally, laboratory data will be analysed qualitatively via comparison of laboratory data to their reference ranges. Values outside the reference range as well as values defined as possible clinically significant will be flagged in the data listings. Dose groups will be compared descriptively with regards to distribution parameters as well as with regards to frequency and percentage of patients with abnormal values or possibly clinically relevant abnormal values.

Clinically relevant findings in laboratory data will be reported as adverse events if judged clinically relevant by the investigator and will be analyzed as such.

It is the investigator's responsibility to decide whether a lab value is clinically significant abnormal or not (at the RPM/DBLM at the latest).

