7.8.3 Vital signs

Descriptive statistics over time including change from baseline will be performed for vital signs (blood pressure, pulse rate). In the vital signs listing, the difference from baseline will also be displayed.

For post-dose measurements of vital signs, descriptive statistics will be calculated by planned time point based on the first value of the subject at that planned time point (or assigned to that planned time point). For baseline value, the last measurement before drug administration will be used.

Body weight will be listed only.

Clinically relevant findings in vital signs as judged by the investigator will be reported as AEs.

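### SAP 6.7 files unscheduled laboratory and vital-sign values taken after the first injection under Visit 2, the baseline visit, so they reach no later visit in the by-visit tables

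*SAP*

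**What the plan says.** - **Premise and rule (SAP 6.7).** "Unscheduled measurements of laboratory data and vital signs data will be assumed to be repeat measurements of the most recent scheduled measurement". It follows that "unscheduled measurements will be assigned to the planned time point of the previous scheduled measurement". Nothing separates values taken before an injection from values taken after it.
- **Baseline (SAP 6.7 and 6.6).** "The baseline value is defined as the last measurement before first administration of BI 836880". Visit 2 is the baseline visit, with screening as the fallback: "Missing baseline laboratory values will be imputed by the respective values from the screening visit".
- **Summaries (SAP 7.8.2 and 7.8.3).** Laboratory statistics, including change from baseline, "will be calculated by visit based on the worst value of the patient at that visit", and values assigned to the visit count as well. Post-dose vital signs are summarised "based on the first value of the subject at that planned time point", again including assigned values.
- **A different rule for other data (SAP Table 6.7: 1).** Efficacy measures and IOP are placed by study day. Days 2 to 43 belong to Visit 3, Week 4.
- **Unscheduled tests are foreseen.** Protocol 6.2.1.2 and 6.2.2.2 allow unscheduled visits for safety at any time. When hepatic injury is suspected and no results are at hand, the protocol asks for the liver parameters, "if necessary in an unscheduled blood test". Visits 2a, 3a and 4a in MRD cohorts 2 and 3 schedule neither laboratory tests nor vital signs, but they allow extra safety procedures (Flow Charts III and IV).

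**The concern.** The premise fits a confirmatory repeat: a doubtful value is measured again and belongs with the value it checks. It does not fit a test prompted by a new symptom after an injection. At Visit 2 the difference matters, because the scheduled measurement precedes the first exposure and the unscheduled one follows it. The rule gives both the same label.

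What is at stake is the by-visit description of laboratory and vital-sign safety in the interval after the first injection. The MRD cohorts have 11, 4 and about 12 patients, so a single displaced value can change the minimum, maximum or mean of a row. A reader of the Week 4 row would see only the scheduled sample and would not know that an abnormal result from two weeks earlier sits under Visit 2 or has dropped out of the table.

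**Working it through.** The plan gives no figure to reproduce here. The check applies the SAP 6.7 rule to the scheduled days in the flow charts.

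**Inputs**
- MRD laboratory tests and vital signs: Days 1, 29, 57, 85, 113, 141 and 169, with a window of ±3 days after Day 1 (Flow Charts II to IV).
- SRD laboratory tests: Days 1, 8, 15, 22, 29 and 43, with a window of ±2 days; none at Visit 3 (Flow Chart I).
- SRD vital signs: the same days plus Visit 3, Day 4 ±1.
- Visit 2 timing: vital signs come before blood sampling (Protocol 5.2.4), and the Visit 2 pharmacokinetic blood is drawn before the injection (Protocol 10.1). That the safety laboratory sample is also pre-dose is inferred from its use as baseline; no section says so outright.

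**Step 1: length of the interval filed under Visit 2.** Length = day of next scheduled test − Day 1, with the range given by the window.

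| Data | Calculation | Range with window |
|---|---|---|
| MRD laboratory and vital signs | 29 − 1 = 28 days | 25 to 31 |
| SRD laboratory | 8 − 1 = 7 days | 5 to 9 |
| SRD vital signs | 4 − 1 = 3 days | 2 to 4 |

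In the MRD part this is the whole interval between the first and second injections, or 28/84 = 33% of the 84 days from Day 1 to Day 85. These are shares of time. The documents do not say how many unscheduled values to expect.

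**Step 2: the two rules side by side (MRD).**

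| Day of unscheduled value | Laboratory or vital signs | IOP (Table 6.7: 1) |
|---|---|---|
| 2 | Visit 2 | Visit 3 |
| 8 | Visit 2 | Visit 3 |
| 15 | Visit 2 | Visit 3 |
| 28 | Visit 2 | Visit 3 |

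**Step 3: what the tables then show.** Take an MRD liver test on Day 10.
- It cannot be the baseline value, because it follows the first administration.
- It is nevertheless assigned to Visit 2. Under the worst-value rule it either stands in the Visit 2 row, giving a change from baseline at the baseline visit, or is left out of the table. In neither case is it at Week 4 or later.
- For a vital sign there are also two readings. If the scheduled Visit 2 reading counts as the first value, the unscheduled one drops out. If the first-value rule covers post-dose readings only, the unscheduled one appears under Visit 2. It reaches no later visit either way.
- SAP 6.1 limits these tables to the on-treatment phase, which begins at first administration. The SAP does not say how that limit combines with the carry-back rule.

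**Step 4: later injections.** The gaps after injections 2 and 3 are 57 − 29 = 28 and 85 − 57 = 28 days. A value from these gaps goes back to Visit 3 or 4. Those visits are already post-baseline, and the worst-value rule lets an abnormal laboratory value into the row. It is dated up to about 28 days early, but it is shown.

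**The case against.** The strongest reply is that little is lost. All individual values are listed (SAP 7), out-of-range laboratory values are flagged, and patients with abnormal values are counted without restriction to a visit (SAP 7.8.2). Clinically relevant findings become AEs. A hepatic injury that meets the criteria is an AESI, reported within 24 hours and tabulated separately. The baseline value is protected by its definition, and no hypothesis is tested. Laboratory handling also follows a sponsor standard, and treatment handling a technical plan, neither of which is available here; either might already deal with the case. All of this stands, and it confines the point to the by-visit and change-from-baseline tables. It does not answer the rule itself, which SAP 6.7 states without exception.

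A second reply is that moving everything to study-day intervals has its own cost. A confirmatory repeat of the Week 4 test taken on Day 44 would be labelled Week 8 and separated from the value it confirms. That is a fair argument for changing the rule at Visit 2 only.

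A reader might also infer more than the documents support:
- **That the safety tables are biased towards no effect in general.** At Visits 3 and 4 a carried-back laboratory value enters a post-baseline row under the worst-value rule, so it is not diluted. Only the first interval is affected.
- **That dose-limiting events could be hidden in the SRD part.** The SRD laboratory interval coincides in time with the 7-day evaluation period, but every DLE criterion in Protocol 5.2.1 is an event in the study eye.
- **That Visit 7 and 8 tests brought forward at withdrawal keep a Week 20 or 24 label.** The protocol says only that "Visit 7 should be scheduled as soon as possible, and also Visit 8/EOT should be performed to assess for safety". These are named visits, the unscheduled-value rule does not address them, and the SAP is silent on their label.

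**Conclusion.** The point holds for the interval between the first injection and the next scheduled test. In that interval, SAP 6.7 assigns unscheduled laboratory and vital-sign values to Visit 2, and they appear at no later visit in the by-visit and change-from-baseline tables. This is a stated rule that misplaces data and that differs, without explanation, from the rule in the same section for IOP.

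Its size is 28 days per MRD patient, 7 days for SRD laboratory tests and 3 days for SRD vital signs, before visit windows. The effect on any table depends on how many such values arise, which the documents do not give. The primary endpoints are not touched.

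The conclusion assumes that the Visit 2 safety laboratory sample is taken before the injection and that the sponsor standards cited do not override SAP 6.7. It is worth correcting because the correction is cheap, not because a safety signal would otherwise go unseen.

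**What to change.** Add to SAP 6.7:
1. No laboratory or vital-sign value taken after the first injection may be assigned to Visit 2.
2. Such a value goes to the first scheduled post-dose visit for that parameter: Visit 3 in the MRD part, Visit 4 for SRD laboratory tests and Visit 3 for SRD vital signs.
3. It also counts in a worst post-baseline row, to be added for both laboratory data and vital signs. For vital signs, say what worst means, for example by showing the highest and the lowest value.
4. The repeat-measurement rule stays as it is for later visits.

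One consequence needs a sentence in SAP 7.8.3. Under the first-value rule, an early unscheduled vital sign moved forward to Visit 3 would displace the scheduled reading. State that the scheduled reading is used in the by-visit row and the unscheduled one in the worst post-baseline row. SAP 6.1 should also say how the on-treatment limit applies to assigned values.

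The cost is SAP wording and a small change to the visit-assignment program; no new data are needed. The downside is a label that can be late. An MRD value from Day 2 would appear under Week 4, planned for Day 29, which is 29 − 2 = 27 days later. A footnote or the listing can give the actual day.

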7. PLANNED ANALYSIS

If not stated otherwise, the SRD part and the MRD part will be analyzed separately. The MRD part consists of three cohorts which will be shown in one table, except for the tables based on ERS which is defined for Cohort 3 only.

Safety analysis (refer to [Section 7.8](#)) will be performed by [REDACTED] and will be presented in Sections 15.1 to 15.4 of the CTR and in Appendix 16.2 and 16.1.13.1.

The prior specified in the CTP, Section 7.1 will be used in all BLRM evaluations.

Descriptive data analysis of PK parameters and concentrations will be performed by the [REDACTED] and will be presented in Section 15.6 of the CTR and Appendix 16.1.13.5.

Descriptive data analysis of biomarker/PD parameters and concentrations will be performed by the [REDACTED] and will be presented in Section 15.7 of the CTR and Appendix 16.1.13.6.

Descriptive data analysis of ADA results will be performed by the [REDACTED] and will be presented in Section 15.8 of the CTR and Appendix 16.1.13.7.

The format of the listings and tables will follow the BI standards (see BI-KMED-BDS-HTG-0045) [\(6\)](#) except for those generated for PK-calculations following BI standards for PK/PD analysis [\(5\)](#).

The individual values of all patients will be listed, sorted by dose group, cohort (MRD part only), patient number, and visit.

The listings will be included in Appendix 16.2 of the CTR.

For end-of-text tables, the set of summary statistics for non-PK parameters is:

| | |
|--------|---------------------------------|
| N | number non-missing observations |
| Mean | arithmetic mean |
| SD | standard deviation |
| Min | minimum |
| Median | median |
| Max | maximum |

For analyte concentrations as well as for all PK parameter, the following descriptive statistics will additionally be calculated:

| | |
|-------|-------------------------------------|
| Nobs | number of observations |
| CV | arithmetic coefficient of variation |
| gMean | geometric mean |
| gCV | geometric coefficient of variation |

| | |
|-----|-----------------|
| P10 | 10th percentile |
| Q1 | 1st quartile |
| Q3 | 3rd quartile |
| P90 | 90th percentile |

Section 7.3.5 of the CTP:

The data format for descriptive statistics of concentrations will be identical with the data format of the respective concentrations. The descriptive statistics of pharmacokinetic parameters will be calculated using the individual values with the number of decimal places as provided by the evaluation program. Then the individual values as well as the descriptive statistics will be reported with three significant digits in the CTR.

Tabulations of frequencies for categorical data will include all possible categories available in the CRF and will display the number of observations in a category, as well as the percentage (%) for each dose group. Percentages will be rounded to one decimal place and will be based on all patients in the respective subject set whether they have non-missing values or not. The category 'missing' will be displayed only if there are missing values.

Units of variables should be given in the titles or column/row descriptors in round brackets (e.g. (mg)).

Exclusion of PK parameters

The ADS ADPP (PK parameters) contains column variables APEX and APEXCO indicating inclusion/exclusion (APEX) of a PK parameter and an analysis flag comment (APEXCO). All analyses based on the PKS will include parameters if they are not flagged for exclusion that is APEX is equal to "Included".

Exclusion of PK concentrations

The ADS ADPC (PK concentrations per time-point or per time-interval) contains column variables ACEX or ACEXCO indicating inclusion/exclusion (ACEX) of a concentration and an analysis flag comment (ACEXCO). Exclusion of a concentration depends on the analysis flag comment ACEXCO. For example, if ACEXCO is set to 'ALL CALC', the value will be excluded for all types of analyses based on concentrations. If ACEXCO is set to 'DESC STATS', the value will be excluded from descriptive evaluations per planned time point/time interval. If ACEXCO contains the addition 'TIME VIOLATION' or 'TIME DEVIATION', the value can be used for further analyses based on actual times. If ACEXCO is set to 'HALF LIFE', the value will be excluded from half-life calculation (and, consequently, any calculation that relies on λz) only; the value is included for all other analyses.

Further details are given in 001-MCS-36-472 "Noncompartmental Pharmacokinetic / Pharmacodynamic Analyses of Clinical Studies" (5) and 001-MCS-36-472_RD-03 "Description of Analytical Transfer Files and PK/PD Data Files" (9).

7.1 DEMOGRAPHIC AND OTHER BASELINE CHARACTERISTICS

Only descriptive statistics are planned for this section of the report, based on the TS.

The data will be summarized by dose group/cohort and in total.

7.2 CONCOMITANT DISEASES AND MEDICATION

Only frequency tables are planned for this section of the report, based on the TS.

Concomitant diseases will be coded using the latest version of the coding system of the Medical Dictionary for Drug Regulatory Activities (MedDRA). Medications will be coded using the World Health Organization Drug Dictionary (WHO-DD). The coding version number will be displayed as a footnote in the respective output.

The diagnoses and medications will be listed. Patients without any concomitant diagnoses or concomitant therapies should be marked with a “No” in the respective column.

Previous and concomitant therapies will be presented per dose group/cohort without consideration of time intervals and treatment periods. In addition, the rescue medication will be presented separately for MRD part.

7.3 TREATMENT COMPLIANCE

Section 4.3 of the CTP:

Compliance will be assured by administration of all trial medication in the study centre under supervision of the investigating physician or a designee. The measured sample concentrations will provide additional confirmation of compliance.

It is not intended to list the compliance separately. Exposure table/listing would quantify whether administration per dose was as per the protocol or not, to indicate any potential compliance issues. Any deviations from complete intake will be addressed in the MQRM/RPM/DBLM and described in the CTR.

7.4 PRIMARY OBJECTIVE ANALYSIS

7.4.1 Main analysis

Section 5.2.1 of the CTP:

For the SRD part and MRD cohort 1:

A DLE is defined as the occurrence of any of the following events in the study eye:

- *Development of sterile endophthalmitis and/or sterile inflammation of the vitreous grade 4+ according to standardization of Uveitis Nomenclature (SUN) working group (WG) grading scheme for anterior chamber cells (see CTP) and a duration of 5 or more days between day 1 and day 8*
- *Visual loss of more than 15 letters at any given time point*
- *Persistent IOP over 30 mmHg for 3 days*

- *Signs of vascular occlusion in a 1st (the main branch) or 2nd degree (the vessel after the first bifurcation of the main branch) retinal vessel, including peripheral retinal hemorrhages in the area supplied by the occluded vessel (hemorrhage of the macula would not be included as this is a symptom of the disease).*

[...]

DLE criteria are not applicable to MRD cohorts 2 and 3. Should an event involving intraocular inflammation/signs of vascular occlusion, decreases in visual acuity, and/or intraocular pressure occur, the event should only be reported as an AESI as described in CTP Section 5.2.8.1, and not as a DLE.

Section 7.3.1 of the CTP:

SRD part:

[figure not shown]
The primary safety endpoint “Number of patients with ocular DLEs from drug administration till EOT” will be analysed descriptively, based on the TS.

[...]

MRD part:

The primary safety endpoint “Number of patients with drug related AEs from drug administration till EOT” will be analysed descriptively, based on the TS.

Descriptive statistics will be provided by dose group/cohort and in total (more details regarding the analysis of AEs are described in [Section 7.8.1](#)).

7.4.4 Supplementary analysis

No supplementary analysis is planned.

7.5 SECONDARY OBJECTIVE ANALYSIS

7.5.1 Key secondary objective analysis

This section is not applicable as no key secondary endpoint has been specified in the protocol.

7.5.2 Secondary objective analysis

Section 7.3.2 of the CTP:

In principle, all secondary endpoints specified in [Section 5.2.2](#) will be analyzed descriptively, based on the TS. The analysis of percent change from baseline in CSFT in the study eye at week 12 (Visit 5) will be done by dose, based on the FAS.

Descriptive statistics for absolute values as well as changes from baseline (percent changes and changes in CSFT and changes in BCVA (study eye)) will be provided by dose group/cohort and in total. Time profiles of mean (\pm SD) absolute values and mean (\pm SD) changes from baseline by cohort as well as individual time profiles (absolute values and changes from baseline) per treatment group/cohort will be provided. For percent changes of CSFT, median and minimum/maximum values will be shown instead.

For those endpoints related to adverse events refer to [Section 7.8.1](#).

Section 5.2.2 of the CTP:

Time to recurrence will be assessed in the MRD part, based on the TS, from last trial drug administration to occurrence of any of the following in the study eye, leading to the use of wAMD rescue medication as decided by the investigator:

- *Increase in CSFT $\geq 75 \mu\text{m}$ with a decrease in BCVA of ≥ 5 letters compared to Visit 5, OR*
- *Decrease in BCVA of > 5 letters compared to baseline (Visit 2), due to worsening wAMD activity,*
OR
- *Decrease in BCVA of ≥ 10 letters compared to the best prior BCVA, due to worsening wAMD activity*

From above criteria, if Visit 5 BCVA/CSFT assessment data is missing, BCVA/CSFT values available earlier than Visit 5 will be used. The last trial drug administration is strictly referring to the third injection, if a patient doesn't complete three injections, the patient will not be evaluated for time to recurrence endpoint and will be censored as per [Table 7.5.2:1](#). The details of censoring rules are listed in the [table](#) below. Kaplan-Meier curves will be estimated by cohort.

Table 7.5.2: 1 Censoring Rules for time to recurrence

| No. | Scenario | Relative Day of Event or Censoring | Outcome |
|-----|--|---|--------------------|
| 1 | A patient meets more than one recurrence rule | Earliest day of recurrence | Event (Recurrence) |
| 2 | A patient completed the treatment and follow-up without recurrence | Last day of follow-up | Censored |
| 3. | SAE after completion of three injection | Day of SAE | Censored |
| 4. | Treatment discontinuation (not completing all three injections) | Time to censoring value is assigned to 1 (day 1 = the first day after last injection) | Censored |

Date: 02 FEB 2024, Version 2.0

BI-VQD-12681-S-G_50-415_AD-01 (5.0)

Boehringer Ingelheim
TRIAL STATISTICAL ANALYSIS PLAN
1336-0007

Page 25 of 36

c31147466-02

Proprietary confidential information © 2024 Boehringer Ingelheim International GmbH or one or more of its affiliated companies.

Boehringer Ingelheim
TRIAL STATISTICAL ANALYSIS PLAN
1336-0007

Page 26 of 36

c31147466-02

Proprietary confidential information © 2024 Boehringer Ingelheim International GmbH or one or more of its affiliated companies.

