#### 2.1.3 Secondary endpoint(s)

[figure not shown]
SRD part:

- Number of patients with drug related AEs
- Number of patients with any ocular AEs in the study eye

MRD part:

- Percent change from baseline in Central Subfield Thickness (CSFT) in the study eye at Week 12 (Visit 5), for each dose
- Change from baseline in BCVA in the study eye at Week 12 (Visit 5)
- Time to recurrence after the last treatment
- Number of patients with any ocular AEs in the study eye

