## 5.2.2 Time to recurrence

Time to recurrence will be assessed in the MRD part from last trial drug administration to occurrence of any of the following in the study eye, leading to the use of wAMD rescue medication as decided by the investigator:

- Increase in CFST  $\geq$  75  $\mu$ m with a decrease in BCVA of  $\geq$  5 letters compared to Visit 5,
- OR
- Decrease in BCVA of  $>$  5 letters compared to baseline (Visit 2), due to worsening wAMD activity,
- OR
- Decrease in BCVA of  $\geq$  10 letters compared to the best prior BCVA, due to worsening wAMD activity

The decision to treat with wAMD rescue medication should be documented in the eCRF.

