### Treated Set (TS)

The TS will consist of all patients who were treated with at least one dose of BI 836880.

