### 7.3.2 Secondary endpoint analyses

In principle, all secondary endpoints will be analysed descriptively, based on the TS. The analysis of percent change from baseline in CSFT in the study eye at Week 12 (Visit 5) will be done by dose, based on the FAS.

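### Time to recurrence: the SAP narrows the Treated Set endpoint to patients with three injections, by day-1 censoring and without declaring the change

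*SAP*

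**What the plan says.** **Protocol.** Section 2.1.3 lists the MRD secondary endpoint as "Time to recurrence after the last treatment". Section 5.2.2 gives the time origin: "Time to recurrence will be assessed in the MRD part from last trial drug administration to occurrence of any of the following". Three criteria follow, each tied to use of rescue medication, and no minimum number of injections is set. On the population, Section 7.3.2 says "In principle, all secondary endpoints will be analysed descriptively, based on the TS"; the exception it names is percent change in CSFT. Section 7.3 defines that set: "The TS will consist of all patients who were treated with at least one dose of BI 836880". Section 6.2.2.2 keeps patients on the visit schedule unless they withdraw consent for follow-up.

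**SAP.** Section 7.5.2 repeats the protocol definition and adds that it is based on the TS. It then says "The last trial drug administration is strictly referring to the third injection". For a patient without three injections, it says that "the patient will not be evaluated for time to recurrence endpoint and will be censored". Row 4 of Table 7.5.2: 1, headed "Treatment discontinuation (not completing all three injections)", sets the censoring time to 1, where day 1 is the first day after the last injection. Kaplan-Meier curves are estimated by cohort.

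SAP Section 4 states that the analyses planned in the protocol will be performed. It records only a clarified baseline definition and a modified responder definition.

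**The concern.** A patient who stops after one or two injections has a last administration, belongs to the TS and remains in scheduled follow-up. Under the protocol wording, a later recurrence with rescue is an event. Under the SAP it cannot be.

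The SAP is also inconsistent with itself. It says these patients are not evaluated, and it also gives them a censored observation. Row 4 counts from the last injection they received, whereas the text above it allows only the third injection to be the last.

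The endpoint has a purpose. Protocol Section 1.3 says the injection-free follow-up is there to study durability and to help guide injection intervals in later studies. A curve labelled TS that describes completers only could be read as covering all treated patients. The protocol also gives routes by which stopping may be linked to outcome. Section 3.3.4.1 includes AEs and the need for interfering drugs among the reasons to withdraw from treatment, Section 5.1 has clinically significant worsening reported as an AE, and Section 4.2.1.1 allows standard-of-care treatment for such worsening in cohorts 1 and 2. If stopping follows worsening, the censoring is informative.

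**Working it through.** The plan states no event count, sample size or power for this endpoint (Table 7.7: 1 concerns CSFT only), so there is no figure to reproduce.

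**1. Follow-up set aside.** Injections are on Days 1, 29 and 57, and EOT is Day 169 (MRD flow charts). Scheduled follow-up from the last dose is:
- one dose: 169 − 1 = 168 days
- two doses: 169 − 29 = 140 days
- three doses: 169 − 57 = 112 days

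Row 4 credits the first two groups with 1 day.

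**2. What day-1 censoring does.** The estimate is S(t) = ∏(1 − dᵤ/nᵤ) over event times u ≤ t, where nᵤ counts patients whose time is at least u. A patient censored at day 1 is in no nᵤ for u > 1. For any recurrence after day 1, the curve is therefore identical to one with these patients deleted. They remain only in the starting N.

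**3. How many patients this could touch.** Table 1.2: 1 (cut-off 25 March 2022, MRD part ongoing) shows fewer than three doses in 2 of 10 patients in cohort 1 (20%) and in 1 + 2 = 3 of 4 in cohort 2 (75%), together 5 of 14 (36%). Some may have been mid-course, so these are upper limits on early stoppers among those 14 patients. The documents give no count for cohort 3.

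**4. Effect of one patient.** Assumptions: one early stopper recurs with rescue 56 days after the last dose, no completer recurs, and everyone else is followed to day 112 after the last dose. Under the SAP rule S(112) = 100% in each cohort. With the clock at the last dose received:
- cohort 2, n=4: 1 − 1/4 = 75%
- cohort 1, n=10: 1 − 1/10 = 90%
- cohort 3, n=12: 1 − 1/12 ≈ 92%

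**5. Direction.** Take cohort 1 with 10 patients, 2 of them early stoppers, and assume 4 of the 8 completers recur on day 84. The SAP rule gives 1 − 4/8 = 50%. With the clock at the last dose received:
- no stopper recurs: 1 − 4/10 = 60%
- one recurs on day 56: (9/10) × (5/9) = 50%
- both recur on day 56: (8/10) × (4/8) = 40%

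The SAP rule can therefore understate, match or overstate the recurrence-free proportion. The event days are assumptions; the documents give none.

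**The case against.** The best defence is that the endpoint was always about durability after the three-injection course. Protocol Section 1.3 describes 12 injection-free weeks after three injections, the first recurrence criterion compares with Visit 5 (four weeks after the scheduled third injection), and MRD patients who do not complete may be replaced. That makes a three-injection analysis a defensible supplementary estimand. It does not make it the TS endpoint that the protocol defines and the SAP repeats, and it does not explain why Section 4 is silent.

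A reader might infer that the rule hides up to 20 points of recurrence in cohort 1 and up to 75 in cohort 2. The documents do not support that. Table 1.2: 1 is a snapshot of an ongoing part, and those figures would need every patient with fewer than three doses to have stopped, recurred and received rescue. A reader might also infer that the curve necessarily overstates durability. Step 5 of the check shows that it need not, and patients may stop for unrelated reasons such as surgery or their own wish.

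Nor are these patients recorded as recurrence-free. Censoring at day 1 treats them as unknown afterwards, and their data remain visible elsewhere: the SAP presents MRD rescue medication separately and lists individual values, and reasons for stopping are to be recorded and reported.

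One practical objection stands. Before Visit 5 an early stopper has no Visit 5 reference for the first criterion, so a corrected rule must supply one. Finally, the endpoint is secondary and descriptive, so no error rate or sample size is affected.

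**Conclusion.** The concern holds as an undeclared narrowing of a secondary endpoint. As written, SAP 7.5.2 yields a completers-only curve presented on the TS, in which a recurrence with rescue after an incomplete course can never be an event. This follows from the text and needs no assumption about the data.

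The size is conditional. In cohorts of about 4 to 12 patients, one reclassified early stopper can move the estimate by about 8 to 25 points under the assumptions of step 4. Whether the curve overstates durability depends on why patients stop and whether they then recur, which the documents do not say. The rule should be corrected before the curve is used to inform injection intervals.

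**What to change.** In SAP 7.5.2 and Table 7.5.2: 1:
- For the TS analysis, start the clock at each patient's last injection actually received. Count a qualifying recurrence with rescue as an event whatever the number of injections. Censor patients without recurrence at the last study-eye assessment.
- For early stoppers before Visit 5, state that the BCVA criteria against baseline and against the best prior value apply. State that the combined CSFT/BCVA criterion uses the last available earlier value. This extends the fallback the SAP already has for missing Visit 5 data.
- Remove the conflict between not evaluating these patients and censoring them.
- Show three-injection completers as a labelled supplementary curve, with the number excluded per cohort.
- Record the handling in SAP Section 4.

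The cost is SAP wording and one extra curve, with no new data collection. The downside is that the main curve mixes patients with one to three doses, which is why the supplementary curve should stand beside it.
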